7.2. Secondary Efficacy Analyses

7.2.1. Endpoint / Variables

7.2.1.1. Rate of Flares

The unadjusted rate of flares per subject-year over 52 weeks will be summarized by treatment group.

7.2.1.2. First Severe SFI Flare

The time to the first severe SFI flare over 52 weeks will be estimated for the treatment groups using the product-limit method.

7.2.1.3. Rebound

Rebound is defined as a SELENA SLEDAI score during the first 24 weeks that exceeds the baseline SELENA SLEDAI score in the subject's respective original parent study.

7.2.1.4. SELENA SLEDAI Scores

SELENA SLEDAI assessments consist of 24 individual weighted items in which signs and symptoms, laboratory tests, and physician's assessment for each of 8 organ systems are given a weighted score and summed if present (marked 'Yes') at the time of the visit or in the preceding 10 days. The maximum theoretical score is 105 (all 24 descriptors

present simultaneously) with 0 indicating inactive disease (marked 'No'), but in practice few subjects have scores > 45 [Buyon, 2005; Petri, 2005].

See Section 13.6.3 for further details.

7.2.2. Summary Measure

7.2.2.1. Rate of Flares

The total number of flares, total subject-years of follow-up in the time interval, and the unadjusted rate per subject-year will be presented.

7.2.2.2. First Severe SFI Flare

See Section 7.1.2.

7.2.2.3. Rebound

The frequencies and percentages of subjects who rebound will be presented by visit through the Week 24 visit, and at any time during the first 24 weeks.

7.2.2.4. SELENA SLEDAI Scores

Summary statistics for the change from baseline in SELENA SLEDAI scores will be presented at each visit in the 52-week treatment phase.

7.2.2.5. Changes in Corticosteroid Use

The frequencies and percentages of subjects who meet each definition will be presented at each visit in the 52-week treatment phase. Steroid doses will be converted to the prednisone-equivalent dose per the derivations in Section. 13.6.3

7.2.3. Population of Interest

The secondary efficacy analyses for all endpoints will be based on the ITT population.

For rebound, the analysis also will be performed by the SELENA SLEDAI score at the BEL116027 Day 0 visit, categorized as ≤ 3 and >3.

7.2.4. Strategy for Intercurrent (Post-Randomization) Events

7.2.4.1. Rate of Flares and First Severe SFI Flare

See Section 7.1.4.

If a subject withdraws from the study, dies or takes a prohibited medication, the subject will be considered as having a SFI flare.

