4.4. Withdrawal Criteria

A subject may voluntarily discontinue participation in this study at any time or may be withdrawn at the discretion of the investigator. Record the primary reason for withdrawal in the electronic case report form (eCRF).

Subjects in the treatment holiday and control groups will be withdrawn from the study for:

- Pregnancy: positive urine pregnancy test.
- Clinically significant, potentially life-threatening (Grade 4) AE that in the clinical judgement of the investigator is possibly, probably or definitely related to belimumab.
- Liver chemistry abnormalities. Refer to details regarding liver chemistry abnormalities and withdrawal as specified in Section 6.4.1.

- Laboratory parameters: Demonstrate clinically important changes in laboratory parameters.
- Prohibited concurrent medication or therapy.

These subjects will complete the Week 52 Exit visit (except for dosing with belimumab) at the time of discontinuation and the16-week follow-up visit assessments at least 16 weeks after the withdrawal visit or last dose of belimumab as appropriate (see Section 6). The 6 month follow-up visit is scheduled only for those subjects in the treatment holiday or control groups.

Subjects in the long-term discontinuation group will be withdrawn from the study for:

- Pregnancy: positive urine pregnancy test.
- Laboratory parameters: Demonstrate clinically important changes in laboratory parameters.
- Have developed clinical evidence of significant, unstable or uncontrolled, acute or chronic diseases not due to SLE (i.e., cardiovascular, pulmonary, hematologic, gastrointestinal, hepatic, renal, neurological, malignancy or infectious diseases), or experienced an adverse event (AE) that could, in the opinion of the principal investigator, put the subject at undue risk.
- Have developed any other medical diseases (e.g., cardiopulmonary), laboratory abnormalities, or conditions (e.g., poor venous access) that, in the opinion of the principal investigator, makes the subject unsuitable for the study.

These subjects will complete the Week 52 visit assessments (see Section 6).

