8.1.2. Primary Efficacy Analysis

Time to first SLE flare will be analyzed using a time-to-event analysis. Time to first SLE flare is defined as the number of days from Day 0 of the BEL116027 study to the first occurrence of a SLE flare. If a subject withdraws from the study or completes week 52 without a SLE flare, time to the first SLE flare will be censored at the time of the last observation (last visit measuring flare). However, if a subject receives prohibited medication during the study, the subject will be considered as having a SLE flare at the time the medication is started. Data observed at or prior to the Day 0 visit will not be included in this analysis.

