7.1.4. Strategy for Intercurrent (Post-Randomization) Events

The disposition of subjects as it relates to intercurrent events is defined as follows:

	Event				
Subject Disposition	Met	Event Date [2]			
Subject has a SFI flare or takes a prohibited medication					
Subject has a SFI flare during the study	Yes	Date of first SFI flare			
[1]					
Subject takes a prohibited medication [1]	Yes	Date of prohibited medication			
Subject does not have a SFI flare and did not take a prohibited medication.					
Subject withdraws from the study or is	No	Censored at last available date where			
lost to follow-up		flare is assessed.			
Subject dies during the study	No	Censored at date of death.			

Subject completes the study	No	Censored at last study visit where flare is
		assessed.

[1] If a subject has a SFI flare and takes a prohibited medication, the event date is the earliest of the first SFI flare date and takes a prohibited medication date.

[2] If a subject meets multiple criteria, then the event date is the earliest date.

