- A reproducible decrease in GFR of >20%, accompanied by proteinuria (>1), and/or cellular (RBC and WBC) casts.
- [Alarcón-Segovia, 2003].

GFR is estimated by the Cockcroft-Gault equation [Cockcroft, 1976] for creatinine clearance in mL/min.

Cockcroft-Gault Equation

$$Cl_{cr} (mL/min) = \frac{(140\text{-}age (yrs)) \text{ x weight (kg)}}{72 \text{ x serum creatinine (mg/dL)}} \text{ x } 0.85 \text{ if female}$$

"Reproducible" requires the criterion to be met at two consecutive visits, including unscheduled visits.

The following table identifies the lab parameters to be used to evaluate the criteria in the renal flare definition above.

Criterion	Parameter	SI Dataset LBTESTCD
Proteinuria	Urine Protein:Creatinine Ratio (mg/mg)	PRTCRT_URQ
GFR	Creatinine Clearance estimated by the Cockcroft-Gault equation (mL/min)	CRTCE_PLR
Cellular casts:		
WBC cellular casts	WBC cellular casts	WBCSTM_URQ
dysmorphic RBCs	dysmorphic RBCs	DRBCM_URQ

SLE Flares and Severe Flares, and Renal Flares

Derivation for rates of SFI flares

• Within a treatment group, the unadjusted flare (severe flare) rate per subject-year in a given phase will be calculated as:

Unadjusted flare (severe flare) rate per subject-year =

total number of flares (severe flares) in the phase / total number of years of follow-up time in the phase.

• The calculation will not include baseline flares in the 116027 study.

Follow-up time derivation for rates of SFI flares		
Phase	Treatment Group	Definition
52-week Treatment Phase	TC, LTD	(Week 52/Exit visit date – Day 0 date + 1)/ 365.25 .
TH Phase	TH	(Week 24/TX re-start date – Day 0 date + 1)/ 365.25 .
RS Phase	TH	(Week 52/Exit visit – Week 24/TX re-start date)/ 365.25.

SELENA SLEDAI Organ System Domains

SELENA SLEDAI assessments consist of 24 individual weighted items in which signs and symptoms, laboratory tests, and physician's assessment for each of 8 organ systems are given a weighted score and summed if present (marked 'Yes') at the time of the visit or in the preceding 10 days. The maximum theoretical score is 105 (all 24 descriptors present simultaneously) with 0 indicating inactive disease (marked 'No'), but in practice few subjects have scores > 45 [Buyon, 2005; Petri, 2005].

Organ system domain scores are the sum of the weights of items within the organ domain as defined in the table below.

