13.7.2.1. Handling of Missing and Partial Dates

Element	Reporting Detail				
General	Partial dates will be displayed as captured in subject listing displays.				
Adverse Events	 The eCRF allows for the possibility of partial dates (i.e., only month and year) to be recorded for AE start and end dates; that is, the day of the month may be missing. In such a case, the following conventions will be applied for calculating the time to onset and the duration of the event: Missing Start Day: First of the month will be used unless this is before the start date of study treatment; in this case the Day 0 visit date (LTD and TH arms) or the study treatment start date (TC arm) will be used and hence the event is considered On-treatment as per Appendix 4: Study Phases and Treatment Emergent Adverse Events. Missing Stop Day: Last day of the month will be used, unless this is after the stop date of study treatment; in this case the study treatment stop date will be used. 				
	• Completely missing start or end dates will remain missing, with no imputation applied. Consequently, time to onset and duration of such events will be missing.				
Concomitant Medications and Medical History	• Medications with partial or missing start and/or stop dates will be assumed to be concomitant unless there is evidence through comparison of partial dates to suggest otherwise, for example if the day is missing, then the month and year will be compared to the month and year of the first dose date of study treatment and if the month and year are the same or later, then the medication will be considered concomitant.				

Element	Reporting Detail
Time to SFI	Evaluated up to Week 52
Flares	 If a subject takes a prohibited medication during the time period being analyzed, the subject will be considered as having a SFI flare at the start date of the prohibited medication.
	 If a subject withdraws from the study, the will be censored at last flare assessment date
	 If a subject dies, censor at the date of death
Time to Renal	Evaluated up to Week 52
Flare	• If a subject withdraws from the study, the will be censored at last renal flare assessment date
	If a subject dies, censor at the date of death
Number of SFI Flares	• If a subject withdraws from the study, dies or takes a prohibited medication, the subject will be considered as having a SFI flare.

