13.11.5. Efficacy Tables

Efficacy	: Tables			
No.	Population	Title	Programming Notes	Priority Headline Results denoted by H
Flares				
2.1.	ITT	Time to First SFI Flare to Week 52	Primary endpoint	Н
2.2.	ITT	SFI Flares per Subject-year from Day 0 to Week 52	Secondary endpoint	
2.3.	ITT	Time to First SFI Severe Flare to Week 52	Secondary endpoint	Н
2.4.	ITT	Time to First Renal Flare to Week 52	Exploratory endpoint	Н
2.5.	ITT	Time to First Renal Flare to Week 52 [1] Among Subjects with Baseline Proteinuria >0.5g/24hr Equivalent	Exploratory endpoint	
Reboun	d and SELENA-	SLEDAI		
2.6.	ITT	SELENA SLEDAI Rebound (LOCF) (52-Week Treatment Phase)	Secondary endpoint	Н
2.7.	ITT	SELENA SLEDAI Change from Baseline (LOCF) (52-Week Treatment Phase)	Secondary endpoint	
PGA		·		
2.8.	ITT	PGA Change from Baseline (52-Week Treatment Phase)	Other/exploratory endpoint	
Prednis	one			
2.9.	ITT	Number of Days of Daily Prednisone Dose >=7.5 mg/day and/or Increased by 25%	Secondary endpoint	
2.10.	ITT	Number of Days of Daily Prednisone Dose <=7.5 mg/day and/or Decreased by 25%	Secondary endpoint	

Efficacy	Efficacy: Tables				
No.	Population	Title	Programming Notes	Priority Headline Results denoted by H	
2.11.	ITT	Prednisone Percent Change from Baseline (52-Week Treatment Phase)	Other/exploratory endpoint		
2.12.	ITT	Prednisone Reduced to <= 7.5 mg/day by Visit (DO/TF=NR) among Subjects with Baseline Prednisone Dose > 7.5 mg/day (52-Week Treatment Phase)	Other/exploratory endpoint		

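### The flare rate counts every withdrawal or death as an SFI flare, adds no follow-up time for it, and plans no split of observed and imputed flares

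*SAP*

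**What the plan says.** SAP 7.2.4.1 covers both the flare rate and time to first severe flare. It refers to 7.1.4 and then adds: "If a subject withdraws from the study, dies or takes a prohibited medication, the subject will be considered as having a SFI flare". The Number of SFI Flares row in SAP Appendix 7 repeats this rule for the count.

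SAP 13.6.3 defines the rate as "total number of flares (severe flares) in the phase / total number of years of follow-up time in the phase". Follow-up ends at the Week 52 or Exit visit for the control (TC) and long-term discontinuation (LTD) groups and for the re-start phase of the treatment holiday (TH) group. For the TH holiday phase it ends at Week 24 or treatment re-start, and Exit is not mentioned.

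For presentation, SAP 7.2.2.1 says: "The total number of flares, total subject-years of follow-up in the time interval, and the unadjusted rate per subject-year will be presented". The only rate table listed in SAP 13.11.5 is Table 2.2, "SFI Flares per Subject-year from Day 0 to Week 52".

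Time to first flare treats the same exits the other way. In SAP 7.1.4 withdrawal is not an event, and its entry begins "Censored at last available date where"; death is censored at its date. The time-to-flare row in Appendix 7 says "If a subject withdraws from the study, the will be censored at last flare assessment date". Protocol 8.1.2 agrees on withdrawal: "If a subject withdraws from the study or completes week 52 without a SLE flare, time to the first SLE flare will be censored". The protocol sets no exit rule for the rate.

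**The concern.** A subject can leave for reasons unrelated to lupus. Protocol 4.4 opens: "A subject may voluntarily discontinue participation in this study at any time or may be withdrawn at the discretion of the investigator". Pregnancy requires withdrawal in all three groups. For LTD the list also includes significant disease not caused by SLE and conditions such as poor venous access. Under SAP 7.2.4.1 each of these is a flare.

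The same subject is then censored in Table 2.1 and counted as a flare in Table 2.2, and nothing specified for Table 2.2 shows how much of the total was imputed. The reported rate depends on exits as well as on disease activity, and a reader cannot separate the two.

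Three details are also unsettled:
- whether a subject who has already flared is given a further flare on leaving;
- how much time a TH subject who withdraws before Week 24 contributes;
- which rule governs time to first severe flare, since the shared sentence in 7.2.4.1 conflicts with the reference to 7.1.4.

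**Working it through.** The plan states no flare rate and no exit rate, so it has no figure to reproduce.

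**Inputs from the documents.** Enrolled numbers are TH 12, TC 29 and LTD 39 (SAP 2.3). Follow-up formulas are in SAP 13.6.3. Over 52 weeks, 74.6% of subjects flared on 10 mg/kg and 81.5% on placebo (SAP Section 2; Protocol Table 4).

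**Assumptions.** 10% of subjects exit (30% for the range), all at Day 182 in TC and LTD. The flare hazard is constant. The tabulated percentages concern first flares, so they only approximate a recurrent rate.

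**Formula.** With F flares counted without exit imputation, D flares imputed for withdrawal or death, and PY subject-years to exit:

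SAP rate = (F + D)/PY = F/PY + D/PY

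The imputation adds D/PY. An exit that follows a prohibited-medication start adds nothing to D, because that start counts as a flare anyway.

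**Time per subject.** Completer: (364 + 1)/365.25 = 0.9993 years. Exit at Day 182: (182 + 1)/365.25 = 0.5010 years.

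**If every exit adds a flare**
- TC, 3 of 29: PY = 26 × 0.9993 + 3 × 0.5010 = 27.49; 3/27.49 = 0.109 per subject-year.
- LTD, 4 of 39: PY = 35 × 0.9993 + 4 × 0.5010 = 36.98; 4/36.98 = 0.108.
- At 30%: TC 9/24.50 = 0.367; LTD 12/32.99 = 0.364.

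**If only flare-free exits add a flare**
- Background from 74.6%: −ln(1 − 0.746) = 1.370 per year. Share still flare-free at exit: exp(−1.370 × 0.501) = 0.503.
- At 10% exits: TC 0.109 × 0.503 = 0.055; LTD 0.108 × 0.503 = 0.054.
- At 30% exits: TC 0.367 × 0.503 = 0.185; LTD 0.364 × 0.503 = 0.183.
- LTD receives no belimumab. On the placebo figure, −ln(1 − 0.815) = 1.687 and exp(−1.687 × 0.501) = 0.43, which gives LTD about 0.108 × 0.43 = 0.046 at 10% exits.

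Relative to 1.370 per year, 10% exits raise the TC rate by 0.109/1.370 = 8% on the first reading and 0.055/1.370 = 4% on the second.

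**TH re-start phase**, assuming all 12 enter and one leaves halfway without an earlier flare in that phase: completer 196/365.25 = 0.5366 years, exit 98/365.25 = 0.2683 years; 1/(11 × 0.5366 + 0.2683) = 1/6.171 = 0.162.

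**TH holiday phase.** The formula gives no end date for a withdrawal before Week 24, so no figure follows from the plan. If an Exit term were added, one exit at Day 84 would give 169/365.25 = 0.4627 and 85/365.25 = 0.2327 years, so 1/(11 × 0.4627 + 0.2327) = 1/5.322 = 0.188.

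**The case against.** The strongest reply is that this is a choice of strategy. Dropout is penalised for the prednisone endpoints too (SAP 7.2.4.3), and the protocol sets no contrary rule for the rate. If exits are related to worsening lupus, a rate without exit imputation would be too low. That stands as a reason to keep the exit-as-flare rate; it does not justify showing only that rate with the imputed count hidden.

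Other planned outputs help. Table 2.1 reports flares with exits censored, Table 1.7 covers time to withdrawal, and Listings 5, 10, 17 and 43 give withdrawal reasons, prohibited medication, deaths and flares. A reader could partly rebuild the split by hand, but none is specified. The table shells are not in the document, so a split there cannot be excluded.

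Several stronger readings are not supported:
- **A large bias.** The 30% figures rest on an assumed exit rate, and the highest also require a new flare for subjects who had already flared.
- **A tilt between groups.** This needs exit rates that differ, and the documents give none.
- **Double counting** when prohibited medication leads to the required withdrawal (Protocol 5.5.2). SAP 7.2.4.1 assigns a single flare to the subject, and the notes in 7.1.4, written for a first event, take the earliest date. One flare is the natural reading.
- **Doubt about prohibited medication** in time to first severe flare. Sections 7.1.4 and 7.2.4.1 both count it as an event.
- **Non-SLE disease and poor venous access as listed withdrawal criteria in every group.** Protocol 4.4 lists them for LTD only.

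**Conclusion.** The point holds as a reporting and specification problem in a secondary endpoint. As written, the rate counts withdrawals and deaths of any cause as flares. In TC, LTD and the TH re-start phase it adds no time for them, and no split is specified. Follow-up for a TH subject who withdraws before Week 24 is undefined.

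The actual size cannot be known from the documents. Under the assumed 10% mid-phase exits, the addition in TC or LTD is about 0.11 per subject-year if every exit adds a flare, and about half that, on a 1.37 per year background, if only flare-free exits do. In a TH group of 12, a single imputed flare is visible.

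Results are descriptive (SAP 2.4) and Table 2.2 is not marked as a headline table, so no test is affected. The harm is a misread rate.

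**What to change.** - In Table 2.2, report the rate from observed SFI flares plus prohibited-medication starts over observed follow-up. Beside it, show the exit-as-flare rate, labelled as such, with the number of imputed flares per group and per TH phase.
- State in SAP 7.2.4.1 whether a subject who has already flared is given a further flare on exit.
- Add an Exit term to the TH holiday-phase follow-up formula in SAP 13.6.3.
- Align the Number of SFI Flares row in Appendix 7.
- State in 7.2.4.1 that time to first severe flare censors withdrawals and deaths as in 7.1.4.

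The cost is SAP wording and one extra row or table. No new data are needed.

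### SAP 7.2.4.1 gives conflicting handling of withdrawal and death for time to first severe SFI flare, and the SAP never says whether a prohibited medication counts as a severe flare

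*SAP*

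**What the plan says.** The endpoint is set in SAP 7.2.1.2: "The time to the first severe SFI flare over 52 weeks will be estimated for the treatment groups using the product-limit method". It is reported in Table 2.3 and Figure 2.2, both marked as headline results in SAP Appendix 11.

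Intercurrent events for this endpoint are handled in the section headed "7.2.4.1. Rate of Flares and First Severe SFI Flare", so one short text governs both a rate and a time-to-event endpoint. It contains two instructions.

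- The first is "See Section 7.1.4". In that table a withdrawal or loss to follow-up without a flare or prohibited medication is not an event. The entry begins "Censored at last available date where" and goes on to name the last flare assessment. A death is not an event either: "Censored at date of death". A prohibited medication is an event, dated "Date of prohibited medication".
- The second is the section's own sentence: "If a subject withdraws from the study, dies or takes a prohibited medication, the subject will be considered as having a SFI flare". It is not restricted to either endpoint and gives no severity.

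The SAP 13.7.3 table on prohibited medications, withdrawals and deaths (its rows print next to 13.7.2.1) treats the two kinds of endpoint separately. Its row for time to SFI flares censors withdrawals at the last flare assessment and, for death, says "If a subject dies, censor at the date of death". Its row for the number of SFI flares repeats the 7.2.4.1 sentence word for word. No row names severe flare.

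Protocol 8.1.2 censors withdrawals for time to first flare and counts a prohibited medication as a flare. It gives no separate rule for severe flare.

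**The concern.** SAP 7.2.4.1 is the only intercurrent-event section that names time to first severe flare. Read alone, it gives opposite answers for a subject who withdraws or dies without a prior event. A programmer must choose, and must also decide whether an imputed flare with no severity belongs in a severe-flare analysis.

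The choice matters because the study is descriptive (SAP 2.4). The estimates are themselves the result, and the groups are small. If the imputation sentence were used here, group differences in Table 2.3 would partly reflect who left the study. It would also produce an incoherent pair of displays. The primary analysis censors the same subjects, so one person could be free of any SFI flare in Table 2.1 yet have a severe one in Table 2.3, although severe flares are a subset of SFI flares.

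**Working it through.** **1. The rules side by side, for a subject with no earlier flare**

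| Situation | SAP 7.1.4 (by cross-reference) | SAP 7.2.4.1, own sentence | 13.7.3, time to SFI flares | 13.7.3, number of SFI flares |
|---|---|---|---|---|
| Withdrawal | Censored, last flare assessment | SFI flare | Censored, last flare assessment | SFI flare |
| Death | Censored, date of death | SFI flare | Censored, date of death | SFI flare |
| Prohibited medication | Event at start date | SFI flare | Event at start date | SFI flare |

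Columns two and three conflict for withdrawal and death. They agree on prohibited medication, but no column says whether that event is severe.

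**2. Does 13.7.3 settle it?** It shows a clear pattern, with censoring for time and imputation for counts. It settles severe flare only if the time-to-SFI-flare row is read as including it. Even then the prohibited-medication rule in that row yields an SFI flare, not a severe one, so that question stays open.

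**3. Weight of one subject.** Enrolment from SAP 2.3 is treatment holiday (TH) 12, treatment control (TC) 29 and long-term discontinuation (LTD) 39. The sum 12 + 29 + 39 = 80 agrees with the stated total. Moving one subject from censored to event changes the crude percentage by 100/n:

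- TH: 100/12 = 8.3 points
- TC: 100/29 = 3.4 points
- LTD: 100/39 = 2.6 points

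**4. Illustration only.** The documents give no severe-flare or dropout rate. Assume about 10% true severe flares and 20% dropout, rounded to whole subjects, with dropouts at mid-study. In TC and LTD half the flares (rounded down) fall before the dropouts and the rest after; the single TH flare falls after them. Product-limit incidence at 52 weeks is then:

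| Group | Flares, dropouts | Dropouts censored | Dropouts counted |
|---|---|---|---|
| TH | 1, 2 | 1/10 = 10.0% | 3/12 = 25.0% |
| TC | 3, 6 | 1 − (28/29)(20/22) = 12.2% | 9/29 = 31.0% |
| LTD | 4, 8 | 1 − (37/39)(27/29) = 11.7% | 12/39 = 30.8% |

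With no true severe flares and the same dropouts, censoring gives 0% in every group. Counting gives 2/12 = 16.7%, 6/29 = 20.7% and 8/39 = 20.5%.

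**The case against.** The strongest reply is that the SAP already answers the question.

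- The 13.7.3 table attaches the disputed sentence only to the number of SFI flares and censors for time to SFI flares.
- SAP 7.1.1 treats severe as one category of SFI flare, so that time row can naturally be read to cover severe flare.
- SAP 7.2.2.2 sends the severe-flare summary to 7.1.2, and 7.2.4.1 sends it to 7.1.4, so the endpoint is modelled on the primary analysis.
- SAP 13.6.3 re-derives flare severity from the subcategory scores. A dropout without such scores offers nothing from which a severe flare could be derived.
- The endpoint is secondary and descriptive, with no test or decision rule attached.

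Most of this stands as evidence of intent. A reader might infer from 7.2.4.1 that the plan reports dropouts as severe flares. The documents do not support that: it would require following the body text over the appendix and adding a severity that the sentence does not give. A reader might also infer that imputed events would swamp true severe flares. That is unsupported too, because the pooled BLISS table gives only percentages with any flare, and LTD subjects may enter at any level of disease activity.

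The reply does not remove the conflict inside 7.2.4.1 or supply a row that names severe flare. It also leaves the status of a prohibited medication unstated.

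**Conclusion.** The point holds as a drafting conflict that should be corrected, with the probable intent visible elsewhere in the SAP. For time to first severe SFI flare, 7.2.4.1 gives incompatible instructions for withdrawal and death without a prior event. The appendix points to censoring but does not name the endpoint. Whether a prohibited medication is a severe-flare event is not stated explicitly anywhere.

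The firm figures are the per-subject shifts of 8.3, 3.4 and 2.6 points. They are crude percentages on the enrolled numbers and arise only if the imputation sentence is applied to this endpoint. The product-limit comparison rests on assumed severe-flare and dropout rates and assumed timing. It shows that the choice of rule can matter in groups this small, not how large the effect would be here.

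**What to change.** - In SAP 7.2.4.1, limit the imputation sentence to the number (rate) of flares.
- In the same section, state that time to first severe SFI flare follows 7.1.4, with withdrawal censored at the last flare assessment and death at the date of death. Keeping the date of death preserves agreement with the primary analysis.
- In the 13.7.3 table, add a row for time to first severe SFI flare that repeats these rules and says explicitly whether a prohibited medication is a severe-flare event.

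The cost is two sentences and one table row. No new data are needed.
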